7.3 Subject Population(s) for Analysis

All-completed population: Only subjects who completed ALL study related procedures and follow-up will be included (Per Protocol) maybe adjusted to subjects who completed the majority of the study visits and procedures. Patients lost to follow-up will be accounted for during calculation of the attrition rate.

8 Safety and Adverse Events

All adverse events occurring during the study, including those not meeting the criteria of an Unanticipated Adverse Device Effect (UADE) will be recorded on the appropriate case report form. Records of these events will be maintained and reports submitted to the FDA and IRB according to the regulatory requirements. Expected clinical adverse events and nonsignificant (not serious) clinical adverse events will not be reported. Expected clinical adverse events and anticipated adverse device effects are those listed in Section 1.5.2.

8.1 Definitions

Unanticipated Adverse Device Effect (UADE)

A UADE is any serious adverse effect on health or safety or any life-threatening problem or death caused by, or associated with, a device if that effect, problem or death was not previously identified in nature, severity, or degree of incidence in the investigational plan or IDE application (including a supplementary plan or application), or any other unanticipated serious problem associated with a device that relates to the rights, safety, or welfare of subjects.

Adverse Effect (Event)

Any untoward medical occurrence in a subject involved in clinical study of an investigational device; regardless of the causal relationship of the problem with the device or, if applicable, other study related treatment(s).

Associated with the investigational device: There is a reasonable possibility that the adverse effect may have been caused by the investigational device.

Life-threatening adverse effect: Any adverse effect that places the subject, in the view of the investigator, at immediate risk of death from the effect **as it occurred**. It does not include a reaction that, had it occurred in a more severe form, might have caused death.

Serious adverse effect: An adverse effect is considered “serious” if, in the view of the investigator, it results in any of the following outcomes:

- death
- a life-threatening AE
- inpatient hospitalization or prolongation of existing hospitalization
- a persistent or significant disability/incapacity
- a congenital anomaly/birth defect.

Unanticipated adverse effect: Any adverse effect, the nature, specificity, severity, or frequency of which is not consistent with the risk information in the clinical study protocol or elsewhere in the current IDE application.

General Physical Examination Findings

At screening, any clinically significant abnormality should be recorded as a preexisting condition. At the end of the study, any new clinically significant findings/abnormalities that meet the definition of an adverse event must also be recorded and documented as an adverse event.

Hospitalization, Prolonged Hospitalization or Surgery

Any adverse event that results in hospitalization or prolonged hospitalization should be documented and reported as an unanticipated adverse device effect unless specifically instructed otherwise in this protocol. Any condition responsible for surgery should be documented as an adverse event if the condition meets the criteria for an adverse event.

Neither the condition, hospitalization, prolonged hospitalization, nor surgery are reported as an adverse event in the following circumstances:

- Hospitalization or prolonged hospitalization for diagnostic or elective surgical procedures for a preexisting condition. Surgery should **not** be reported as an outcome of an adverse event if the purpose of the surgery was elective or diagnostic and the outcome was uneventful
- Hospitalization or prolonged hospitalization required to allow efficacy measurement for the study
- Hospitalization or prolonged hospitalization for therapy of the target disease of the study, unless it is a worsening or increase in frequency of hospital admissions as judged by the clinical investigator.

Post-study Adverse Event

All unresolved adverse events should be followed by the investigator until the events are resolved, the subject is lost to follow-up, or the adverse event is otherwise explained. At the last scheduled visit, the local investigator should instruct each subject to report, to the local investigator, any subsequent event(s) that the subject, or the subject's personal physician, believes might reasonably be related to participation in this study. The local investigator should notify the Mayo IRB of any death or adverse event occurring at any time after a subject has discontinued or terminated study participation that may reasonably be related to this study. The IRB should also be notified if the local investigator should become aware of the development of problems, cancer or of a congenital anomaly in a subsequently conceived offspring of a subject that has participated in this study.

Preexisting Condition

A preexisting condition is one that is present at the start of the study. A preexisting condition should be recorded as an adverse event if the frequency, intensity, or the character of the condition worsens during the study period.

Unanticipated Problems Involving Risk to Subjects or Others (UPIRTSO)

Any unanticipated problem or adverse event that meets all of the following three criteria:

- Serious: Serious problems or events that results in significant harm, (which may be physical, psychological, financial, social, economic, or legal) or increased risk for the subject or others (including individuals who are not research subjects). These include: (1) death; (2) life threatening adverse experience; (3) hospitalization - inpatient, new, or prolonged; (4) disability/incapacity - persistent or significant; (5) birth defect/anomaly; (6) breach of confidentiality and (7) other problems, events, or new information (i.e. publications, DSMB reports, interim findings, product labeling change) that in the opinion of the local investigator may adversely affect the rights, safety, or welfare of the subjects or others, or substantially compromise the research data, **AND**
- Unanticipated: (i.e. unexpected) problems or events are those that are not already described as potential risks in the protocol, consent document, not listed in the Investigator's Brochure, or not part of an underlying disease. A problem or event is "unanticipated" when it was unforeseeable at the time of its occurrence. A problem or event is "unanticipated" when it occurs at an increased frequency or at an increased severity than expected, **AND**
- Related: A problem or event is "related" if it is possibly related to the research procedures.

Adverse Event Reporting Period

For this study, the study treatment follow-up period is defined as 90 days following the last administration of study treatment.

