1.5.2 Anticipated Risks and Benefits

The study adds minimal risks to procedures that patients are already scheduled to undergo (EMR). A potential risk of ECM is injury during application to the resection site. We propose the use of endoscopic clips or X-tac to carefully attach each corner of the square ECM material to healthy esophageal tissue surrounding the defect site. This will be carried out by an endoscopist with expertise in esophageal disease and endoscopic therapy. The potential benefit of this includes mitigation of the ensuing inflammatory process. Patients undergoing endoscopic resection return for routine endoscopic follow-up in 8-12 weeks. Injection with saline at this time is safe and will be performed by an experienced endoscopist. Saline is typically resorbed by the tissue within minutes of injection.

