3.4 Primary Safety Endpoints

Primary safety endpoints include overall survival, incidence of all serious adverse events including unanticipated adverse device effects, incidence of technical and device failures and malfunctions, and quality of life as measured by the above dysphagia questionnaires.

4 Subject Selection, Enrollment and Withdrawal

Patients will be recruited from the Barrett's Esophagus clinic where patients with Barrett's esophagus, esophageal cancer, and/or esophageal nodules are referred for consideration of endoscopic evaluation and management. Patients with advanced esophageal cancer are typically not referred as they warrant chemoradiotherapy or palliative care, and are not candidates for endoscopic management. Thus, this clinic presents a selective population to screen from, and one we anticipate will be able to provide the proposed number of subjects for this study. It is estimated 75-100 patients with esophageal lesions undergoing EMR will be screened to ultimately meet study enrollment goals.

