4.4 Early Withdrawal of Subjects

4.4.1 When and How to Withdraw Subjects

Subjects will be withdrawn from the study if any adverse events related to EMR, or application of ECM occurs, including major bleeding, perforation, or infection. Patients will also be withdrawn if after EMR the patient proceeds to esophagectomy.

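### The hospitalisation rule in Section 8.1 conflicts with that section's own UADE definition, so the UADE component of the primary safety endpoint could be miscounted

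*Combined protocol and SAP*

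**What the plan says.** **Hospitalisation rule (Section 8.1, paragraph on hospitalization and surgery).** The rule reads: "Any adverse event that results in hospitalization or prolonged hospitalization should be documented and reported as an unanticipated adverse device effect". A qualifier follows: the rule yields where the protocol gives a specific contrary instruction. A list of exceptions comes next, introduced by "Neither the condition, hospitalization, prolonged hospitalization, nor surgery are reported as an adverse event in the following circumstances". There are three: elective or diagnostic procedures for a preexisting condition; admission needed to measure efficacy; and treatment of the target disease, unless the investigator judges that it has worsened or that admissions have become more frequent.

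**UADE definition (Section 8.1).** The effect must be serious and "caused by, or associated with, a device if that effect, problem or death was not previously identified" in the investigational plan or IDE application. Association is defined as a reasonable possibility that the investigational device was the cause.

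**Expected events (Section 8, opening paragraph).** "Expected clinical adverse events and anticipated adverse device effects are those listed in Section 1.5.2". For the device, Section 1.5.2 says: "A potential risk of ECM is injury during application to the resection site". It does not list the usual complications of EMR. Section 4.4.1 does foresee events related to EMR or to applying the matrix, "including major bleeding, perforation, or infection", and Section 1.1 discusses stricture at length.

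**Endpoint and reporting.** Section 3.4 includes among the primary safety endpoints the "incidence of all serious adverse events including unanticipated adverse device effects". Sections 8.3 and 8.3.2 set a limit of 10 working days for UADE reports to the FDA, and Section 8.3 sets 5 working days for the IRB.

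**The concern.** Section 8.1 gives two ways to decide whether an event is a UADE. The definition asks three questions: is it serious, is it associated with the device, and was it unforeseen? The hospitalisation rule asks only whether an adverse event led to admission. Every patient in this trial has an EMR, which can lead to admission in either arm, and only one arm receives the extracellular matrix (ECM). If the rule is followed literally, admissions for procedural complications enter the UADE count whether or not a device was placed. That count is a named part of the primary safety endpoint and starts regulatory reporting deadlines. Two staff members applying the document in good faith could classify the same admission differently.

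The second strand is whether EMR complications are anticipated. The answer depends on which section one consults, so the test for an unforeseen event has no single reference either.

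**Working it through.** The plan states no figure on this point, so the check is to run one case through the rules. The only number needed is the 10 patients per group in Section 7.1.

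**Test case: a control patient (observation only, Section 6.2) admitted for bleeding after EMR.**

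1. *Is it an adverse event?* Yes. Section 8.1 counts any untoward occurrence whatever its cause, and Section 8.2 records events in both groups.
2. *Is it serious?* Yes. Inpatient admission is a seriousness criterion in Section 8.1.
3. *Does an exception apply?* Not clearly. The admission is not elective or diagnostic, not for efficacy measurement, and not plainly treatment of the target disease: it treats a complication of the procedure.
4. *Result under the hospitalisation rule:* UADE.
5. *Result under the UADE definition:* not a UADE. With no matrix placed, there is no reasonable possibility that it caused the event.
6. *Does the protocol say which rule governs?* No. Section 8.2 requires a causality review but does not say that it overrides the hospitalisation rule. Section 8.3 has UADEs reported as necessary, and Section 8.3.2 requires the FDA form once an effect has been determined to be a UADE. Neither says how the two classification rules rank.

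**Is the bleeding expected?**

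| Source | Reference used | Result |
|---|---|---|
| Section 8, opening | Section 1.5.2 only | Not listed, so unexpected |
| Section 8.1, UADE | Investigational plan or IDE application | Arguably identified (Section 4.4.1) |
| Section 8.1, unanticipated adverse effect | Risk information in the protocol or IDE application | Arguably identified |
| Section 8.1, UPIRTSO | Risks described in the protocol, consent document or Investigator's Brochure, or part of the underlying disease | Arguably identified |

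Perforation and infection (Section 4.4.1) and stricture (Section 1.1) give the same split.

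**Effect on the counts.**

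- SAE count for the test case: 1 under either rule, so the change is 0.
- UADE count: 1 under the hospitalisation rule, 0 under the definition.
- UADE rate in a 10-patient arm: 1/10 − 0/10 = 10 percentage points. The shift is the same for an ECM patient admitted for a complication judged unrelated to the matrix.

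**How likely is at least one such label?** The documents give no admission rate, so the rates p below are assumptions. With independent patients, the chance of at least one is 1 − (1 − p)^n. For example, 1 − 0.95^10 = 0.401.

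| Assumed p | Expected among 10 controls (10p) | At least one, n = 10 | At least one, n = 20 |
|---|---|---|---|
| 1% | 0.1 | 9.6% | 18.2% |
| 2% | 0.2 | 18.3% | 33.2% |
| 5% | 0.5 | 40.1% | 64.2% |
| 10% | 1.0 | 65.1% | 87.8% |

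Here p is the rate of admission for an EMR complication unrelated to the matrix. The n = 20 column applies the same rate to both arms.

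**The case against.** The best defence is that the rest of Section 8 can be read as limiting the rule. The rule yields to contrary instruction, and the UADE definition, the causality review in Section 8.2 and the determination step in Section 8.3.2 could be taken as that instruction. On this reading a control patient is never a UADE. The reading is reasonable, but no text establishes it. The qualifier asks for a specific instruction, and none of these sections mentions hospitalisation as an exception. Section 8.3.1 restricts which events go to the IRB; it does not change how an event is classified.

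Four stronger readings are tempting, and the documents do not support them:

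- *Every hospitalisation is a UADE.* The rule covers adverse events that result in admission, with a qualifier and three exceptions.
- *EMR complications are definitively unexpected.* That follows from Section 8 with Section 1.5.2, but the wider references in Section 8.1 point the other way. It is a contradiction, not a settled rule. What the IDE application identifies cannot be checked from these documents.
- *The primary safety endpoint as a whole is miscounted or cannot be compared by arm.* Total SAE incidence is the same under either rule. Section 7.2 specifies no analysis of UADEs by arm, so the 10-point shift arises only if such a rate is tabulated.
- *FDA reports for control patients are automatic.* Section 8.3.2 ties the form to a determination that the effect is a UADE.

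It is also fair to say that over-classification in a 20-patient feasibility study errs towards more reporting. This lowers the stakes but does not tell staff which rule to apply.

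**Conclusion.** The concern holds as an internal contradiction. The hospitalisation rule and the UADE definition give different answers for the same event, including for patients with no device, and the protocol does not rank them. The reference for anticipated events is contradictory as well. The consequence is confined to the UADE component of the primary safety endpoint and the reporting attached to it. That component could be miscounted if the hospitalisation rule is applied over the definition, by 10 percentage points per patient so labelled in an arm of 10. SAE incidence is not affected. The size rests on the planned 10 per arm. The probabilities of at least one mislabelled patient rest on assumed admission rates and are illustrations only. The point should be corrected because the change is small and the component is a named endpoint.

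**What to change.** 1. **Section 8.1, hospitalisation rule.** Reword along these lines: an adverse event that leads to or prolongs hospitalisation is recorded as an SAE in either arm, and is classified as a UADE only if it meets the UADE definition in this section. Keep the three exceptions.
2. **One reference for anticipated events.** Reconcile Sections 1.5.2, 4.4.1, the opening of Section 8, and the UADE, unanticipated-effect and UPIRTSO definitions in Section 8.1, so that all point to the same risk information.
3. **Protect serious events.** Adding EMR complications to Section 1.5.2 is not enough by itself. The opening of Section 8 says expected events are not reported, so a bare list could suppress reporting of a serious perforation or bleed. The matrix is fixed with clips or X-tac, so some such events could be device-related. State that listed events are still recorded and reported as SAEs when serious, and that a device-associated event still counts as unanticipated if its kind, severity or frequency goes beyond what was identified.

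The cost is a few sentences in a protocol amendment. The downside is slightly fewer default UADE reports; with item 3 in place, serious events remain recorded and reported.

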1.6 Anticipated Duration of the Clinical Investigation

Screening and enrollment will be performed at the time of consent for their endoscopy and anticipated resection. In eligible patients randomized to ECM placement, the endoscopy will require an additional 5-10 minutes for application of ECM. Follow-up will occur per standard of care in all patients undergoing EMR, that is endoscopy in 8-12 weeks or sooner for patient symptoms (e.g., dysphagia).

2 Study Objectives

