3.1 General Design

This is a randomized study on the efficacy of ECM in promoting constructive healing following endoscopic resection (EMR). 20 patients anticipated to undergo endoscopic resection will be recruited in the outpatient setting from the Barrett's Esophagus Unit. Prior to endoscopy, patients will complete a standardized questionnaire (Mayo Dysphagia Questionnaire) and the physician will use the Mellow-Pinkas scale to assess baseline dysphagia. Patients with lesions that lift and are amenable to cap-assisted EMR will be randomized to receive ECM to the defect site vs. standard of care. All patients should be on standard of care double dose proton-pump inhibitor therapy (Omeprazole 40mg PO daily or the equivalent); if this has not been initiated they will be provided a prescription .

In both groups, patients will be brought back for repeat standard of care clinic and endoscopic assessments in 12-16 weeks, or sooner if needed. A clinical dysphagia assessment will be performed with repeat of the above questionnaires. Endoscopy will involve inspection of the wound site, and images in white-light and electron chromoendoscopy will be taken for blinded evaluation later. Submucosal saline injection at the wound site will be performed to determine its ability to lift.

Any patients receiving esophageal dilations will be noted. Patients requiring esophagectomy will be excluded from the primary objective of the study but their surgical specimen at the site of endoscopic resection will be evaluated for evidence of constructive healing.

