5.8.4 Return or Destruction of Study Device

We will order clinical supply as needed and dispose of unused supply. We do not anticipate needing to return supplies.

6 Study Procedures

6.1 Visit 1

Patients will be recruited from the Barrett's Esophagus Clinic. Patients referred for endoscopic evaluation of Barrett's esophagus with high grade dysplasia, esophageal nodules or early esophageal cancer and are scheduled for EMR, will be screened using inclusion and exclusion criteria outlined above. Patients meeting inclusion criteria will be consented for study inclusion and will be asked to complete the Mayo Dysphagia Questionnaire.

6.2 Visit 2

Visit 2 refers to the procedure during which the patient will undergo planned EMR of the esophageal lesion. Visits 1&2 may take place on the same date. Patients will undergo endoscopy and those amenable to standard EMR will be randomized to receive ECM or receive standard of care (i.e., observation). ECM will be applied to patients in the manner described above.

6.3 Visit 3

All patients will be scheduled to return in approximately 12-16 weeks (up to 6 months) following EMR for follow-up endoscopic evaluation. Patients will repeat the Mayo Dysphagia Questionnaire prior to endoscopy. During endoscopy, the EMR site will be inspected and multiple pictures will be taken in white-light as well as electron chromoendoscopy (i.e., narrow band imaging). Thereafter, standard submucosal saline injection of the healed EMR site will be performed, and the endoscopist will record whether no lift, a partial lift, or complete lift was observed. Symptomatic structuring will be treated with standard pneumatic dilation.

Schedule of Events			
Study Activity	Baseline*	Procedure*	Follow-up procedure (3-4 months)
Consent	X		
History	X		X
Physical Exam	X	X	X
Disease State Symptom Survey	X		X
Concurrent Medications	X	X	X
Adverse Events		X	X
Serious Adverse Events		X	X

*Baseline and Procedure may be on the same date/visit.

7 Statistical Plan

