8.2 Recording of Adverse Events

At each contact with the subject, the investigator must seek information on adverse events by specific questioning and, as appropriate, by examination. Study subjects will be routinely questioned about adverse effects at study visits. Information on all adverse events should be recorded immediately in the source document, and also in the appropriate adverse event section of the case report form (CRF). All clearly related signs, symptoms, and abnormal diagnostic, laboratory or procedure results should be recorded in the source document.

All adverse events occurring during the study period must be recorded. All observed or volunteered adverse effects (serious or non-serious) and abnormal test findings, regardless of the treatment group if applicable or suspected causal relationship to the investigational device or if applicable other study treatment or diagnostic product(s) will be recorded in the subjects' case history. For all adverse effects sufficient information will be pursued and obtained as to permit; an adequate determination of the outcome, an assessment of the causal relationship between the adverse effect and the investigational device or, if applicable other study treatment or diagnostic product. The clinical course of each event should be followed until resolution, stabilization, or until it has been ultimately determined that the study treatment or participation is not the probable cause. Serious adverse events that are still ongoing at the end of the study period must be followed up, to determine the final outcome. Any serious adverse event that occurs after the study period and is considered to be at least possibly related to the study treatment or study participation should be recorded and reported immediately.

Causality and severity assessment

The investigator will promptly review documented adverse effects and abnormal test findings to determine 1) if the abnormal test finding should be classified as an adverse effect; 2) if there is a reasonable possibility that the adverse effect was caused by the investigational device or other study treatments; and 3) if the adverse effect meets the criteria for a serious adverse effect.

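### The 90-day adverse event period in 8.1 ends before most Visit 3 dates, has no start point for controls, and is not reconciled with 8.2 or the schedule

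*Combined protocol and SAP*

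**What the plan says.** Section 8.1 gives the only numerical safety window in the plan: "the study treatment follow-up period is defined as 90 days following the last administration of study treatment". Section 3.4 lists "incidence of all serious adverse events including unanticipated adverse device effects" among the primary safety endpoints and gives it no window of its own.

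The follow-up visit is timed in several ways. Section 3.1 says "patients will be brought back for repeat standard of care clinic and endoscopic assessments in 12-16 weeks, or sooner if needed". Section 5.4 repeats 12-16 weeks. Section 6.3 has "approximately 12-16 weeks (up to 6 months) following EMR". The schedule of events heads the column 3-4 months and marks adverse events and serious adverse events there. Section 1.6, however, describes "endoscopy in 8-12 weeks or sooner for patient symptoms", and 1.5.2 also gives 8-12 weeks.

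Section 8.2 requires every adverse event in the study period to be recorded, whatever the arm or suspected cause, with questioning at study visits. Its rule for what comes later begins "Any serious adverse event that occurs after the study period and is considered to be at least possibly related", and the relation may be either to the treatment or to taking part in the study. Section 6.2 describes the control arm as observation.

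**The concern.** An incidence needs a start, an end and a rule for what counts, and these must be the same in both arms. Section 8.1 supplies an end that comes before most of the visits at which the outcome is assessed, and a start that exists in only one arm. Section 8.2 supplies a different boundary, the study period, without saying when it closes.

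At stake is a named primary safety endpoint. Two analysts working from the same case report forms could produce different counts of serious adverse events, each with support in the text. The second endoscopy is also a point of risk in its own right, because the healed site is injected and may be dilated, and the 90-day period would usually miss it.

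**Working it through.** The 90 days is a definition, so the plan has no calculation to reproduce. The check is to put it on the same calendar as Visit 3.

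**Inputs.** Day 0 is the index EMR. For an ECM patient this is also the day of last administration, because the scaffold is placed at that endoscopy (5.2, 5.3, 6.2). Days are counted inclusively and each date in a window is weighted equally; the weighting is an assumption.

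**End of the period.** 90 / 7 = 12.86 weeks. Against each stated window:

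- *12-16 weeks (3.1, 5.4, 6.3).* 12 × 7 = 84 and 16 × 7 = 112, giving 112 − 84 + 1 = 29 dates. Days 91 to 112 are 22 dates, and 22 / 29 = 76%. The longest gap is 112 − 90 = 22 days, which is 22 / 112 = 20% of that patient's follow-up.
- *12 weeks to 6 months (6.3), with 6 months taken as 182 or 183 days.* 92 of 99 or 93 of 100 dates fall after day 90, which is 93% either way. The longest gap is 92 or 93 days, about half of that patient's follow-up (92 / 182 = 51%).
- *3-4 months (schedule).* With 30-day months (days 90-120), 30 of 31 dates fall after day 90. With 30.44-day months (days 91-122), all 32 do.
- *8-12 weeks (1.5.2, 1.6).* Days 56-84: 0 of 29 dates.

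**Visit 3 procedures.** An event caused by the saline injection or a dilation cannot precede the visit. In the 12-16 week window it is therefore outside the period for at least 22 of 29 dates. On the other 7 dates (days 84-90), at most 90 − 84 = 6 days of cover remain.

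**Start of the period.** An ECM patient has an administration date. A control has none. Section 5.2 places randomisation in the same procedure, directly after resection, so a date common to both arms exists, but 8.1 does not use it.

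**What governs after day 90.** Take a serious adverse event on day 100 in a patient whose Visit 3 is on day 112.

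- If the study period is the 90 days, the event is recorded only if judged at least possibly related.
- If the study period runs to Visit 3, the event is recorded in either arm whatever its cause.

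The text does not choose between these. With 10 patients per group (7.1), one event counted or not moves an arm's incidence by 1 / 10 = 10 percentage points.

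**Who judges relatedness.** Section 5.7 is headed masking but describes only randomisation. The one masked assessment described is of the endoscopic images (3.1, 3.3). Section 8.4 provides for unblinding, but no section says that the investigator judging relatedness is masked.

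**The case against.** A reader might infer that the safety comparison is already cut off at day 90 and that late events are kept for ECM patients and lost for controls. The documents do not support that.

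- No section equates the 90 days with the study period of 8.2.
- Several passages point the other way. The schedule marks adverse events at the follow-up procedure. Section 8 asks for all events during the study. The post-study paragraph in 8.1 has patients told at their last scheduled visit to report anything that follows, which suggests that post-study time starts after that visit.
- Recording under 8.2 does not depend on arm or cause, and its later rule extends to study participation. Controls participate and are also injected at Visit 3, so a late control event can qualify.
- Both arms have the same natural day 0, the EMR procedure, so no difference in window length is shown.
- Section 7 specifies no between-arm safety test that could be shown to be biased.
- The 76% is a share of calendar dates. It is not a share of events or of follow-up time, and it is zero under the 8-12 week timing.

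All of this stands, and it limits the consequence. It does not remove the conflict. The 90-day sentence sits under the heading for the adverse event reporting period, so it is the natural source of a window for 3.4. Collecting events at a visit does not settle which of them the endpoint counts.

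**Conclusion.** The point holds as a conflict between stated rules. The period in 8.1 closes before 76% of the possible visit dates in the 12-16 week window and about 92 days before a 6-month visit, and it names no start for the observation arm. That rests on the timings in 3.1, 5.4 and 6.3; if the 8-12 week timing in 1.5.2 and 1.6 governed, only the missing start and the undefined study period would remain.

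The consequence is conditional. If 90 days is applied as the window, the serious adverse event endpoint is truncated, and inclusion of later events depends on a relatedness judgement, not described as masked, that could lean differently by arm. The documents do not show that this will happen, nor do they give a rate of late events from which to size it. The primary efficacy analysis and the sample size are unaffected. The point should be corrected because it concerns a primary safety endpoint and is cheap to settle.

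**What to change.** In 8.1, define the adverse event period for every randomised patient as running from the index EMR procedure through completion of Visit 3, and use the same definition for the study period in 8.2. State that all serious adverse events in that period count towards the 3.4 endpoint regardless of relatedness. Keep the 8.2 rule on later, possibly related serious events as an addition; it would also cover a complication of the Visit 3 procedures that appears after the patient has left. Say where the period ends for a patient who never has Visit 3.

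The sponsor should also reconcile the follow-up timings in 1.5.2, 1.6, 3.1, 5.4, 6.3 and the schedule with 8.1 and 8.2. Which timing applies is the sponsor's decision; the proposed definition works with any of them.

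The cost is a sentence or two in 8.1 plus that reconciliation. The schedule already collects adverse events at the follow-up procedure, so no visit, form or patient is added.
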